**Table 3 Dosing Schedule and Total Expected Volume Based on Weight at Baseline of the Present Study**

Weight	Dose	Total Daily Dose	Total Expected Volume
12-20 kg	30 mL (6 g) BID	60 mL (12 g)	60 mL x Number of Days Expected to be Dosed
>20-35 kg	40 mL (8 g) BID	80 mL (16 g)	80 mL x Number of Days Expected to be Dosed
>35-50 kg	50 mL (10 g) BID	100 mL (20 g)	100 mL x Number of Days Expected to be Dosed
>50 kg	60 mL (12 g) BID	120 mL (24 g)	120 mL x Number of Days Expected to be Dosed

BID = twice daily

**Table 4 Conversion of Height of Remaining Liquid (cm) into Volume (mL).**

Height of Remaining Liquid (cm)	Estimated Volume (ml)	Height of Remaining Liquid (cm)	Estimated Volume (ml)
0.5	18	7.0	248
1.0	35	7.5	266
1.5	53	8.0	283
2.0	71	8.5	301
2.5	89	9.0	319
3.0	106	9.5	336
3.5	124	10.0	354
4.0	142	10.5	372
4.5	159	11.0	389
5.0	177	11.5	407
5.5	195	12.0	425
6.0	212	12.5	443
6.5	230	13.0	460

## **11. PRIOR, CONCOMITANT, AND POST-TREATMENT MEDICATION**

Prior medication is defined as any medication with stop dates prior to the date of the first dose of double-blind study drug from study ACP-2566-005. Concomitant medication is defined as any medications that are ongoing at the first dose of study drug or with a start date between the dates of the first and last doses of study drug, inclusive, in study ACP-2566-005. Post-treatment medication is defined as any medication with a start date after the date of the last dose of study drug. Medications will be coded using WHO Drug Global Dictionary March 2020 or newer version.

The number and percentage of subjects taking prior, concomitant and post-treatment medications will be tabulated separately by each drug class (ATC Level 3) and medication preferred term, treatment group of the antecedent DB study and overall for Safety Analysis Set. Multiple medication usage by a subject in the same category will be counted only once. Listings of the prior, concomitant and post-treatment medications will also be provided.

### **COVID-19 Infection Related Medications**

Concomitant medication analyses described above will also be tabulated and listed by relationship to COVID-19 Infection (Not related to COVID-19 Infection vs. Related to COVID-19 Infection).

## **12. EFFICACY ANALYSES**

Unless otherwise specified, all efficacy analyses will be performed using the Safety Analysis Set. No hypothesis testing is planned. Descriptive summaries of all efficacy endpoints will be presented.

### **12.1 Efficacy Variables**

#### Secondary Efficacy Endpoints

- RSBQ total score – change from Baseline to Weeks 12, 52, 104, and 130
- CGI-I score at Week 12 (assessing improvement from the Baseline of the antecedent study, ACP-2566-004)

Change from Baseline to Weeks 52, 104, and 130 in:

- CSBS-DP-IT Social
- Overall Quality of Life Rating of the ICND

Change from Baseline to Weeks 12, 52, 104, and 130 in:

- RTT-HF score
- RTT-AMB score

Change from Baseline to Weeks 12, 52, and 130 in:

- RTT-COMC score
- RTT-VCOM score

Change from Baseline to Weeks 12, 52, 104, and 130 in:

- CGI-S score

Change from Baseline to Weeks 52 and 130 in:

- RTT-CBI total score (items 1-24)

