### **3. STUDY DESIGN**

#### **3.1 General Study Design**

This is a multi-center, open-label, long-term study of trofinetide to monitor the safety and efficacy of continuing trofinetide therapy. Subjects who complete the preceding open-label study (ACP-2566-004) will be eligible to enroll in the present study.

[figure not shown]
The duration of participation for individual study subjects will be approximately 32 months, or less than 32 months if: 1) trofinetide becomes commercially available for the treatment of Rett syndrome or 2) if development of trofinetide for Rett syndrome is discontinued. The Sponsor may discontinue the study for any reason. Note that not all subjects entering the present study will be treated for 32 months. It is anticipated that the time from which the first subject enters the present study until the predicted time that trofinetide receives marketing authorization and is marketed will be 29 months. Therefore, subjects who enter the present study, for example, 6 months after the first subject enters, will receive treatment with trofinetide for approximately 23 months before the study is terminated based on the anticipated date of commercial availability of trofinetide.

Legally acceptable representatives (LARs)/subjects must be consented prior to the procedures being performed at the end of treatment (EOT) visit of the antecedent study. The EOT visit of the antecedent study will serve as the Baseline visit of the present study. The data gathered at the EOT visit of the antecedent study serves as the baseline data of the present study. The duration of participation for individual study subjects will be up to approximately 32 months with a safety follow-up period of 30 (+4) days. Approximately 28 sites will participate in this study.

The study will have two periods ([Figure 1](#)):

- Treatment period: up to approximately 32 months
- Safety follow-up period: 30 days

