### **3.4 Determination of Sample Size**

The sample size of this open-label study is not determined based on statistical considerations. However, subjects enrolled in the present study are those who have completed the antecedent study, ACP-2566-004, and rolled over to the present study. Since approximately 180 subjects are to be enrolled in the ACP-2566-004 study and it is expected 85% of these subjects will complete Study ACP-2566-004 and rollover to the present study, the number of subjects in the present study will be approximately 153.

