### **5.5 Analysis Visit Windows**

Efficacy and safety will be summarized by analysis visit as presented in Table 2 below.

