#### **5.5.1 Unscheduled Assessments**

Both Scheduled and Unscheduled assessments, including the assessments at early termination visits, will be included for planned timepoint analyses based on the above analysis visit windowing rules. All assessments will be presented in data listings.

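### Five efficacy scales have no SAP 12.1 timepoint for some windows in which their end-of-treatment score can fall; read literally, those scores are listed but not summarised

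*SAP*

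**What the plan says.** - **Windows.** SAP 5.5 states: "Efficacy and safety will be summarized by analysis visit as presented in Table 2 below". Table 2 has four post-baseline windows, the same for every scale: Week 12 (Day 2–224), Week 52 (Day 225–546), Week 104 (Day 547–819) and Week 130 (Day 820–940). It has no end-of-treatment or last-visit row.
- **Final visit.** The schedule (protocol Table S-1, SAP 20.1) has one shared column for Week 130, EOT and ET. RTT-COMC, RTT-VCOM, RTT-CBI, CSBS-DP-IT and ICND are all marked in it.
- **Assignment of final scores.** On ratings made on or off the visit schedule, SAP 5.5.1 says: "including the assessments at early termination visits, will be included for planned timepoint analyses based on the above analysis visit windowing rules". The same section puts all assessments in the listings.
- **Reported timepoints.** For RTT-COMC and RTT-VCOM, SAP 12.1 gives "Change from Baseline to Weeks 12, 52, and 130 in". For RTT-CBI it gives "Change from Baseline to Weeks 52 and 130 in". CSBS-DP-IT Social and ICND are given at Weeks 52, 104 and 130. SAP 13.1 tabulates the endpoints listed in 12.1.
- **Protocol endpoint.** Protocol 2.2.1 defines the endpoint for all five scales as change from Baseline to the end of treatment visit. SAP 18 declares no change from the protocol's analyses.

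**The concern.** The by-visit lists in SAP 12.1 follow the visits at which each scale is scheduled. The windows in Table 2 do not: they take in a final visit on any day. A subject who leaves, or who is still in the study at closure, is rated on all five scales on a day set by her own entry and exit. If that day falls in a window that 12.1 omits for a scale, the score is assigned to an analysis visit with no row for it.

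RTT-COMC, RTT-VCOM and RTT-CBI are not scheduled at Week 104, so the EOT/ET score is their only scheduled assessment after Week 52. Leaving it out of the tables would remove most of the long-term information on these scales for the subjects affected. It is also the score that the protocol endpoint names. SAP 14.3 provides a last post-baseline summary for laboratory values, but the SAP has no counterpart for efficacy.

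**Working it through.** **Inputs.** Windows: SAP Table 2. Timepoints per scale: SAP 12.1. Anticipated closure 29 months after first entry, and an example subject treated for about 23 months: SAP 3.1 and protocol 3.1. Other durations given: 30 months (protocol 1.4) and up to about 32 months (protocol 3.1, SAP 3.1). Month length: 365.25/12 = 30.44 days, the SAP 5.1 conversion. The documents give no distribution of entry times, so uniform entry over 6, 9, 12 or 18 months is assumed.

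**Step 1: reproduce Table 2.** Target day = 7 × week + 1 gives 85, 365, 729 and 911. Midpoints of adjacent targets are 225, 547 and 820. These give the windows 2–224, 225–546, 547–819 and 820 onward, as stated; the upper limit of 940 is taken from the table. Windowed post-baseline days: 940 − 2 + 1 = 939.

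**Step 2: cross the windows with SAP 12.1.**

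| Scale | Windows without a listed timepoint | Days | Share of 939 |
|---|---|---|---|
| RTT-COMC, RTT-VCOM | Week 104 (547–819) | 273 | 29.1% |
| RTT-CBI | Week 12 (2–224) and Week 104 (547–819) | 223 + 273 = 496 | 52.8% |
| CSBS-DP-IT, ICND | Week 12 (2–224) | 223 | 23.7% |
| RSBQ, RTT-HF, RTT-AMB, CGI-S | none | 0 | 0% |

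CGI-I is reported at Week 12 only, but it is not scheduled at EOT/ET, so it has no final score to lose.

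**Step 3: the SAP's example subject.** Entry 6 months after the first subject with closure at 29 months gives 23 months: 23 × 30.44 = about Day 700. This lies in Day 547–819.

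**Step 4: share of subjects staying to closure with EOT in Day 547–819.** In months, 547/30.44 = 17.97 and 820/30.44 = 26.94. For closure at C months, the affected entry times run from C − 26.94 to C − 17.97 months after the first subject. For uniform entry over L months:

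share = [min(L, C − 17.97) − (C − 26.94)] / L

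| Closure C | Affected entry (months) | L = 6 | L = 9 | L = 12 | L = 18 |
|---|---|---|---|---|---|
| 29 months | 2.06 to 11.03 | 66% | 77% | 75% | 50% |
| 30 months | 3.06 to 12.03 | 49% | 66% | 75% | 50% |
| 32 months | 5.06 to 14.03 | 16% | 44% | 58% | 50% |

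For example, C = 29 and L = 6 gives (6 − 2.06)/6 = 66%; C = 32 and L = 9 gives (9 − 5.06)/9 = 44%.

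**Step 5: the Day 2–224 gap.** 225/30.44 = 7.39 months. With closure at 29 months, a final visit before Day 225 needs either departure within about 7 months or entry more than 29 − 7.39 = 21.6 months after the first subject. It therefore concerns mainly early leavers. The documents give no dropout rate, so it is not quantified.

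**The case against.** The strongest reply is that the omission is not certain. SAP 5.5 summarises efficacy by Table 2 visit with no exception by scale. SAP 5.1 presents change from baseline for each continuous measure across the study's timepoints. Protocol 9.5.3 summarises all these scales by timepoint. SAP 13.1 does not say that only the 12.1 timepoints are shown. This stands: a programmer could reasonably produce every window for every scale. But 12.1 with 13.1 is the more specific text, and 5.5.1 refers to planned timepoint analyses. Two readings yield different tables, and the SAP does not choose between them.

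A reader might also infer more than the documents support:

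- *That the scores are lost.* They are not; all assessments are listed.
- *That most final scores on these scales would go unsummarised.* This depends on a closure date that SAP 3.1 words as a forecast ("It is anticipated that the time from which the first subject enters the present study until the predicted time that trofinetide receives marketing authorization") and on an assumed entry pattern. The share can be as low as 16% at 32 months, and it is about half with 18-month entry at any of the three closure dates. It counts only subjects who stay to closure. RTT-COMC is not required at off-site visits, so some of its scores may never be collected.
- *That SAP 12.1 is why few subjects reach the Week 130 row.* A small Week 130 row follows from staggered entry with a common closure and applies equally to RSBQ, CGI-S, RTT-HF and RTT-AMB. It is not part of this point.

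Finally, the protocol classes efficacy as exploratory, and SAP 12 says: "No hypothesis testing is planned. Descriptive summaries of all efficacy endpoints will be presented". No primary or safety result is affected. That limits the priority. It does not settle the inconsistency.

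**Conclusion.** The point holds as an inconsistency with a foreseeable consequence. Under the literal reading of SAP 12.1 and 13.1, EOT/ET scores on Day 547–819 for three scales and on Day 2–224 for three (RTT-CBI in both groups) have no planned summary, contrary to the general wording elsewhere and to the protocol's end-of-treatment endpoint. The documents' own example subject falls in the first gap, so this is an ordinary case under the plan's own forecast.

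The size is conditional. Of subjects staying to closure, 50–77% would be affected at 29 months, 49–75% at 30 months and 16–58% at 32 months, under uniform entry over 6 to 18 months. The true entry pattern and dropout are not in the documents, so no count out of the planned 153 or so subjects can be given. Priority is low to moderate.

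**What to change.** In SAP 12.1 and 13.1:

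1. State that every scale is summarised at every Table 2 visit at which it has data. This adds Week 104 rows for RTT-COMC, RTT-VCOM and RTT-CBI, and Week 12 rows for CSBS-DP-IT, ICND and RTT-CBI. Label these six rows *EOT/ET or unscheduled assessments only*.
2. Add an end-of-treatment (last post-baseline) row for each of the nine scales whose protocol 2.2.1 endpoint is change to that visit, as SAP 14.3 already does for laboratory values. By-visit rows alone would still split that endpoint across windows.

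The cost is a short SAP edit and some descriptive rows; no new data or testing is needed. SAP 5.1 presents changes against two baselines, so the six by-visit rows become twelve and the nine end-of-treatment rows eighteen. The added by-visit rows hold a selected group, namely leavers and subjects at closure, and should not be read alongside scheduled-visit means as if they were comparable. The label is there to say so.

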2.2.1 Exploratory Endpoints

The exploratory endpoints for this study are:

- Rett Syndrome Behaviour Questionnaire (RSBQ) total score – change from Baseline to end of treatment visit
- Clinical Global Impression–Improvement (CGI-I) Score at the Week 12 visit (assessing improvement from Baseline of the antecedent Study ACP-2566-004)

Change from Baseline to end of treatment visit in:

- Communication and Symbolic Behavior Scales-Developmental Profile™ Infant-Toddler Checklist – Social Composite Score (CSBS-DP-IT Social)
- Overall Quality of Life Rating of the Impact of Childhood Neurologic Disability (ICND) Scale
- Rett Syndrome Clinician Rating of Hand Function (RTT-HF)
- Rett Syndrome Clinician Rating of Ambulation and Gross Motor Skills (RTT-AMB)
- Rett Syndrome Clinician Rating of Ability to Communicate Choices (RTT-COMC)
- Rett Syndrome Clinician Rating of Verbal Communication (RTT-VCOM)
- Clinical Global Impression–Severity (CGI-S)
- Rett Syndrome Caregiver Burden Inventory (RTT-CBI) Total Score (items 1-24)

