9.5.3 Efficacy Analyses

Descriptive summary statistics for RSBQ (absolute values and change from Baseline), CGI-I (absolute values, assessed by comparing to the status at Study ACP-2566-004 baseline), CGI-S, CSBS-DP-IT, each of the four Rett Syndrome Clinician Rating scales, RTT-CBI, and ICND Quality of Life score absolute values and change from Baseline will be summarized by timepoint.

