### 5.1 General Data Reporting Conventions

Continuous variables will be summarized using the following descriptive statistics: number of subjects, mean, standard error (SE), standard deviation (SD), median, minimum, and maximum. For descriptive summaries of efficacy changes from baseline, the 95% confidence interval (CI), calculated as mean  $\pm$  1.96\*SE, will be presented. Unless specified otherwise, means, medians, and CIs will be presented to one more decimal place than the raw data, and the SDs and SEs will be presented to two more decimal places than the raw data. In general, the maximum number of decimal places is 4 and values will be truncated to 4 decimal places in situations where there are more than 4 decimal places. Wherever possible data will be decimal aligned.

Height, weight and BMI will be presented with a maximum of one decimal place.

Categorical variables will be summarized by the number of subjects and the percentage of subjects in each category; the number of subjects and the percentage of subjects with missing data will be summarized for demographic and baseline characteristics (if applicable). Categories with zero counts will not have zero percentages displayed. For demographic summaries, percentages will be calculated by using the total number of subjects in the given treatment group of the antecedent double-blind (DB) study (ACP-2566-003) as the denominator. Percentages will be presented with one decimal place.

Duration in months will be calculated as ([the number of days / 365.25] \*12).

Clinical laboratory assessment values that are collected with “<” or “>” signs will generally be analyzed as the numerical value without the sign in tables and figures. In listings, these data will be reported as collected with the sign.

For each continuous measure in safety and efficacy analyses, change from baseline results will be presented by treatment group of the antecedent DB study ACP-2566-003 and overall in two ways:

1. Main analysis: using the baseline of this study, as defined in [Section 5.5](#), to report the changes across the timepoints of this open-label Study ACP-2566-005.
2. Exploratory analysis: using the baseline from the antecedent study, ACP-2566-003, to report the changes across the timepoints of this open-label Study ACP-2566-005.

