**Table 2 Analysis Visit Windows**

Analysis Visit	Target Study Day	Study Day Interval
Baseline (Day 1)	1	$\leq 1$
Day 1 Post First Dose*	1	1
Week 12	85	2 – 224
Week 52	365	225 – 546
Week 104	729	547 – 819
Week 130	911	820 – 940

\*For ECG assessments only; other assessments post-first dose on Day 1 will go to the Week 12 analysis visit window.

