### **5.5.2     Multiple Measurements within Visit Windows**

In the event that more than one assessment falls within a given window, the assessment closest to the target study day will be selected for the by-visit analysis. If two assessments are equidistant from the target study day, then the chronologically last assessment will be used.

For safety analyses where the extreme values should be selected (e.g., overall post-Baseline minimum, overall post-Baseline maximum, and potentially clinically important values), all non-missing post-Baseline values should be considered, regardless of whether the value is selected for the by-visit summaries. All assessments will be presented in data listings.

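### The protocol defines nine exploratory endpoints as change to the end-of-treatment visit, but the SAP tabulates fixed weeks only and does not deliver them when that visit falls before Day 820

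*SAP*

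**What the plan says.** Protocol 2.2.1 words the RSBQ endpoint as a change to the end-of-treatment visit and introduces eight more scales with "Change from Baseline to end of treatment visit in": CSBS-DP-IT Social, ICND quality of life, RTT-HF, RTT-AMB, RTT-COMC, RTT-VCOM, CGI-S and RTT-CBI. Only CGI-I is tied to a named week (Week 12). Protocol 9.5.1 says that all endpoints will be summarized. Protocol 9.5.3 then asks that "absolute values and change from Baseline will be summarized by timepoint".

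SAP 12.1 lists the same nine scales at fixed weeks. For RTT-CBI the entry is "Change from Baseline to Weeks 52 and 130 in". RTT-COMC and RTT-VCOM have Weeks 12, 52 and 130. The other six have Week 104 as well as Weeks 52 and 130. SAP 13.1 tabulates the endpoints listed in 12.1.

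SAP 5.5 adds a general rule: "Efficacy and safety will be summarized by analysis visit as presented in Table 2 below". Table 2 gives windows for Baseline, Day 1 post-dose (ECG only) and Weeks 12, 52, 104 and 130, with none for EOT. SAP 5.5.1 states that scheduled, unscheduled and early-termination scores "will be included for planned timepoint analyses based on the above analysis visit windowing rules". When several scores share a window, SAP 5.5.2 says "the assessment closest to the target study day will be selected for the by-visit analysis". SAP Section 18 declares no changes from the protocol's analyses.

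**The concern.** The schedules in both documents label the last visit as Week 130 and EOT/ET together, which suggests that the Week 130 row is the EOT endpoint. The SAP does not assign scores by visit label, however. It assigns them by study day.

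Both documents expect stops before Week 130. They anticipate 29 months from first entry to marketing and say that someone entering 6 months after the first subject would be treated for about 23 months.

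For a subject whose EOT falls before Day 820, the protocol's endpoint is therefore not summarized. Her final score either sits in an earlier week's row, mixed with subjects who are continuing, or is passed over for an older score and appears only in listings. No combination of the planned by-visit rows recovers the change to EOT for these subjects.

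**Working it through.** **Inputs.** SAP Table 2 target days are 85, 365, 729 and 911. Its windows are Days 2–224, 225–546, 547–819 and 820–940. The stop times used are 29 months (SAP 3.1), 30 months (Protocol 1.4) and about 32 months (Protocol synopsis, study duration). SAP 5.1 converts months with 365.25/12 = 30.4375 days.

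**The plan's own figure.** The window boundaries are midpoints of adjacent targets: (85+365)/2 = 225, (365+729)/2 = 547 and (729+911)/2 = 820. All three match Table 2, including the Day 820 cut.

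**Where an EOT score goes**, if earlier visits were on target:

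| EOT day | Six scales with a Week 104 visit | RTT-COMC, RTT-VCOM, RTT-CBI |
|---|---|---|
| 225–365 | Week 52 row | Week 52 row |
| 366–546 | replaced by the Day 365 score | replaced by the Day 365 score |
| 547–729 | Week 104 row | no row, or Week 104 row |
| 730–819 | replaced by the Day 729 score | no row, or Week 104 row |
| 820–940 | Week 130 row | Week 130 row |

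The six scales are RSBQ, CGI-S, RTT-HF, RTT-AMB, CSBS-DP-IT and ICND. The other three have no Week 104 visit, so their result on Days 547–819 depends on which SAP text governs. If SAP 12.1 fixes the rows (narrow reading), the score reaches no table. If SAP 5.1 and 5.5 put every Table 2 window in every table (broad reading), it is kept under Week 104. EOT before Day 225 arises only through dropout.

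The replacing score is older by at most 819 − 729 = 90 days in the Week 104 window and 546 − 365 = 181 days in the Week 52 window.

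**Single subjects, 29-month stop.** The first entrant's EOT is 29 × 30.4375 = Day 883. Day 819 is 819/30.4375 = 26.9 months, so anyone entering more than 29 − 26.9 = 2.1 months after the first has EOT before Day 820.

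- Entry at 3 months: 26 × 30.4375 = Day 791, replaced by the Day 729 score on the six scales.
- Entry at 6 months (the plan's example): 23 × 30.4375 = Day 700, kept on the six scales but in the Week 104 row.
- Entry at 12 months: 17 × 30.4375 = Day 517, replaced by the Day 365 score on all nine scales.

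**Shares of subjects.** The documents give no entry span. I assume uniform entry over 6, 12 or 18 months, no dropout, visits on target and EOT no later than Day 911. EOT day = (stop − entry month) × 30.4375, rounded to a whole day.

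Worked case, 29-month stop and 12-month entry:

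- Week 130 row: (882.69 − 819.5)/30.4375 = 2.08 months; 2.08/12 = 17.3%.
- Days 730–819: 90/30.4375 = 2.96 months; 24.6%.
- Days 547–729: 183/30.4375 = 6.01 months; 50.1%.
- Remainder, Days 517–546: 8.0%.
- In no by-visit table: 24.6 + 8.0 = 32.6%.

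Six scales, percent in the Week 130 row / an earlier row / no by-visit table (rounded, so rows may not sum to 100):

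| Stop | 6-month entry | 12-month entry | 18-month entry |
|---|---|---|---|
| 29 months | 35/16/49 | 17/50/33 | 12/39/50 |
| 30 months | 51/0/49 | 26/50/25 | 17/33/50 |
| 32 months | 85/0/15 | 42/33/25 | 28/33/38 |

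RTT-COMC, RTT-VCOM and RTT-CBI, percent in no table, broad reading / narrow reading:

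| Stop | 6-month entry | 12-month entry | 18-month entry |
|---|---|---|---|
| 29 months | 0/65 | 8/83 | 33/83 |
| 30 months | 0/49 | 0/74 | 33/83 |
| 32 months | 0/15 | 0/58 | 22/72 |

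Among displaced subjects on the six scales, the tabulated score is on average 45.5 to 88.9 days older than the EOT score across the nine scenarios.

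**The case against.** The strongest reply is that the SAP does what Protocol 9.5.3 asks: it summarizes by timepoint, at every week each scale is scheduled. On that view the conflict lies inside the protocol, between 2.2.1 and 9.5.3, and Section 18 of the SAP is literally correct. Part of this stands: the tension does begin in the protocol. But 9.5.3 describes a presentation and does not withdraw the endpoint in 2.2.1, and 9.5.1 requires all endpoints to be summarized. Listings do not meet that.

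It is also fair that choosing the on-target score for a Week 52 or Week 104 row is ordinary, correct windowing. What is wrong is that no other row carries the EOT score.

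The percentages rest on assumed entry spans and no dropout, and the ranges are wide. The 32-month rows apply a stated maximum duration as a calendar stop. The high figures for the three scales without a Week 104 visit need the narrow reading, and the general wording of SAP 5.5 supports the broad one. These points limit how precisely the size is known. They do not touch the missing row.

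Treatment of 32 months would be 32 × 30.4375 = Day 974, past the last window at Day 940. The schedule, however, places the final visit at Week 130 + 7 days (911 + 7 = Day 918), so I do not rely on that.

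Finally, the endpoints are exploratory, no hypothesis is tested, and a pooled EOT row mixes treatment durations. All of this is true, and it limits the severity.

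**Conclusion.** The concern holds. Followed as written, the SAP does not deliver nine protocol-named endpoints for any subject whose EOT falls before Day 820, and both documents expect such subjects. This conclusion follows from the text and needs no assumption about accrual.

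The number affected does depend on accrual. Under the stated assumptions, 12% to 85% of subjects have their EOT score in the Week 130 row, and 15% to 50% have it in no by-visit table on the six scales. For the other three scales the untabulated share is 0% to 33% on the broad reading and 15% to 83% on the narrow one. If an earlier scheduled visit was missed, the EOT score would take that week's row instead of being displaced.

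The consequence is limited to descriptive exploratory efficacy. Primary safety is not affected and no data are lost. It should be fixed, because it concerns all but one of the study's efficacy endpoints.

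**What to change.** In SAP 12.1 and 13.1, add one end-of-treatment row of change from Baseline for each of the nine scales, using the score from the subject's EOT/ET visit whatever its study day. Do not carry an earlier visit forward when that score is missing. Report n for each scale, since Protocol 6.1.7 allows RTT-COMC to be skipped off-site, and summarize time on treatment alongside. Leave the by-visit tables and Table 2 windows as they are. In Section 18, note that the fixed-week summaries supplement the Protocol 2.2.1 endpoint.

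The cost is SAP wording and one row per efficacy table, with no new data. SAP 14.3 already plans a last-post-Baseline summary for laboratory values, so a comparable layout exists, though its definition differs from the EOT/ET visit. The drawback is that the row pools different treatment durations, which the time-on-treatment figures make visible.
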